12.2.2.4 Assessment of Outcome

The result or conclusion of the AE will be assessed and recorded by the Investigator as:

- Fatal
- Not recovered/not resolved (the AE has not improved, or patient has not recuperated)
- Recovered/resolved (the AE has improved, or patient has recuperated)
- Recovered/resolved with sequelae (recuperated but retained pathological conditions resulting from the AE)
- Recovering/resolving (the patient is improving but the AE has not yet resolved)
- Unknown (not known, not observed, not recorded, or refused)

12.2.2.5 Action Taken with Study Drug

The action taken regarding study drug will be assessed by the investigator as:

- Dose not changed (dose completed)
- Dose interrupted (IV infusion was temporally modified by temporarily stopping the infusion; slowing of the rate of infusion should also be classified as interrupted)
- Drug withdrawn (IV infusion was modified through termination of the infusion)

A response option for increasing or decreasing the dose is not an available course of action in this study.

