6.2.4 Safety Endpoints

The safety endpoints of this study are:

- Safety and tolerability of SEL-212 compared to placebo as assessed by AEs, AESI, serious AEs (SAEs), deaths, and discontinuations due to AEs
- Additional safety assessments will include review and evaluation of laboratory testing including hematology, coagulation, chemistry, urinalysis; eGFR; UACR; vital signs; immunogenicity analyses; 12-lead ECGs; and physical examination findings.

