7.1.3 Follow-Up Phase

Patients will be followed for safety monitoring (30 + 4 days) after their final study drug infusion and will have an End of Study visit by telephone at the following times: either (1) at the completion of the 6 month Treatment Phase or (2) at early termination if the patient voluntarily withdraws consent. Patients who terminate the study prematurely will continue to be followed by having all Early Termination assessments performed. Patients who terminate the study prematurely who are unable to be on-site for the Early Termination visit will be contacted by telephone for safety follow-up.

If withdrawn from study drug, regardless of reason, the patient will continue study visits to the end of Treatment Period 6.

Figure 1: Study Schematic

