8.3.3 Enrolled Patient Withdrawal and Discontinuations

8.3.3.1 Withdrawal Procedures

Early termination from the study occurs when an enrolled patient withdraws consent or is lost to follow-up. The reason for withdrawal will be evaluated and recorded in the case report form (CRF) and source documents.

Patients may withdraw consent at any time. Reason(s) for withdrawal of consent, failure to return for the necessary visits, or termination from the study should be documented. All patients that withdraw early upon termination should have the Early Termination visit assessments completed (i.e., End of Study assessments) ([Appendix A](#)), if the assessments pose no risk to the patient and the patient allows such assessments.

 Selecta Biosciences	PHASE 3 STUDY: SEL-212/302 VERSION: 7.1	EFFECTIVE DATE 15 DEC 2022
---	--	-------------------------------

The Investigator should consult with the Sponsor/medical monitor prior to withdrawing study drug from any patient in the study. Since this is a multiple-dose study, once dosed, patients generally should not be terminated by the Investigator. The patient should be followed through the end of Treatment Period 6, unless the patient withdraws consent or is lost to follow-up. In situations where continued participation in certain aspects of the study pose a risk to the patient, with consultation with the medical monitor, the Investigator should discontinue those procedures that pose a risk and should continue to collect data and conduct those assessments that do not put the patient at risk through the end of Treatment Period 6. Patients with compliance issues or major deviations that effect data quality will also continue to be followed through the end of Treatment Period 6 collecting as much data on the patient as possible, unless otherwise indicated by the Sponsor.

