12.2.2 Recording Adverse Events

Patients will be encouraged to spontaneously report any changes in health from the time of signing the ICF through completion of the study. Study staff will also inquire about any changes in the patient's health.

All AEs will be recorded in the source document and the CRF. It is the responsibility of the Investigator to review all documentation (e.g., hospital progress notes, laboratory, and diagnostics reports) for the presence of AEs and for a complete evaluation of known AEs.

At minimum for each AE, the Investigator will evaluate and report the event name/term/description, onset (date and time), resolution (date and time), event severity/intensity, relationship to study drug, action taken in regards to study drug, whether the event is an SAE, and whether or not it caused the patient to discontinue the study. The event time is only required while the patient is in the clinic.

During the Screening Phase (from time informed consent is signed to immediately before dosing) any clinically significant changes in the patient's health will be recorded in the patient's medical history and will not be considered as AEs.

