**Statistical Analysis Plan**  
 Sponsor: Selecta Biosciences  
 Protocol No.: SEL-212/302

---

An overall summary will be provided of the number and percentage of patients reporting AEs, TEAEs, treatment-related (possibly related and related) TEAEs, serious TEAEs, treatment-related serious TEAEs, AEs of special interest (AESIs), infusion reactions (this is a study drug-related AE that occurs within 24 hours after initiation of study drug infusion), TEAEs leading to study drug withdrawal and TEAEs leading to death. In the overall summary, additionally, the number and percentage of patients with at least one severe TEAE, with at least one moderate TEAE but no severe TEAE and with only mild TEAEs will be provided. Additional analysis will be performed on a subset of infusion reactions (this is a study drug-related AE that occurs within 1 hour after completion of study drug infusion) that fulfil the criteria of an Allergic Reaction/Hypersensitivity according to the Rheumatology Common Toxicity Criteria, version 2.0. Any gout flare which occurs within 24 hours after initiation of study drug infusion will be listed as a gout flare and not as an infusion reaction.

The number and percentage of patients with TEAEs / treatment-related TEAEs / serious TEAEs / AESIs / TEAEs leading to study drug withdrawal/ will be summarized by SOC and PT for each treatment group, overall SEL-212 and total. TEAEs will also be summarized by SOC and PT for maximum intensity and maximum causality for each treatment group, overall SEL-212 and total.

Exposure-adjusted event rates based on i) patients and also based on ii) events by treatment group, overall SEL-212 and total will be provided for patients with at least one related TEAE, at least one SAE, at least one TEAE of special interest and also for specific TEAEs of special interest. For SAEs and AESIs that occur in  $\geq 2\%$  of individuals, as well as the most common TEAEs, the rate difference of exposure-adjusted event rates between the two treatment groups together with the 95% confidence interval will be provided; this will also be presented for the two treatment groups combined vs. placebo.

i) Exposure –adjusted event rate in treatment group A based on patients = Number of all patients with at least one event in treatment group A / Total sum of the treatment exposure time of all patients in treatment group A.

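### Protocol 12.2.2.5 defines drug withdrawal as ending one infusion, while SAP 10.3 tabulates adverse events that led to withdrawal of study drug, so stops between infusions may be under-counted

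*Protocol*

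**What the plan says.** Protocol 12.2.2.5 lists the actions an investigator can record for an AE:

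- "Dose not changed (dose completed"
- an interrupted dose, which covers both a pause in the infusion and a slower rate
- "Drug withdrawn (IV infusion was modified through termination of the infusion"

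It adds that raising or lowering the dose is not available as a response. It lists no 'not applicable' option.

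Protocol 12.2.2 has one further AE-level item on discontinuation: "whether or not it caused the patient to discontinue the study". Leaving the study is defined narrowly in Protocol 8.3.3.1: "Early termination from the study occurs when an enrolled patient withdraws consent or is lost to follow-up". Protocol 7.1.3 keeps patients who are off drug in the study: "If withdrawn from study drug, regardless of reason, the patient will continue study visits to the end of Treatment Period 6".

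On the output side, Protocol 6.2.4 names "deaths, and discontinuations due to AEs" among the safety endpoints. The overall AE summary in SAP 10.3 includes "TEAEs leading to study drug withdrawal and TEAEs leading to death", and the same section repeats the drug-withdrawal counts by SOC and PT. Protocol 13.5.2 refers only to withdrawal, without saying whether drug or study is meant.

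**The concern.** The definition and the output are at different levels. The action item describes what happened to one infusion. The table is meant to show which AEs ended treatment. Doses are 28 days apart, so an AE can arise well after one infusion, lead to no further dosing, and never touch an infusion in progress. Taken at its word, the protocol gives the investigator no option for that event.

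At stake are a named safety endpoint and the breakdown by term. If withdrawals due to AEs are taken from this item as defined, AEs that begin between infusions could be missing from the table, and the AE and disposition tables could give different counts.

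**Working it through.** No figure in the plan needs reproducing, and the documents give no rate of AE-related stops or of terminated infusions. The check sets the sections side by side.

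**1. Does any action option cover a permanent stop between infusions?** Option 1 concerns a completed dose, option 2 a temporary stop or slowing, and option 3 an infusion that is ended. None refers to later doses. An AE that begins after a completed infusion and rules out the next one fits option 1 literally, and option 3 not at all.

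**2. Does the other AE item fill the gap?** No. Protocol 12.2.2 asks about leaving the study, which Protocol 8.3.3.1 confines to withdrawn consent or loss to follow-up. Protocol 7.1.3 has patients off drug continue their visits whatever the reason. For such a patient the correct answer to the 12.2.2 item is no.

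**3. Does the protocol itself generate such cases?** Yes.

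- Protocol 12.1.8.7 ends study treatment for severe or critical COVID-19. It also does so, at any severity, when COVID-19 is treated with antivirals, anti-cytokine agents or JAK inhibitors. Patients may continue assessments.
- Protocol 12.2.1.5 counts drug-related AEs up to 24 hours after the start of infusion as infusion reactions. Protocol 10.7 gives the infusion times: 0.5 h + 1 h for the first component, a gap of up to 0.5 h, then at least 2 h for the second. If the second runs its minimum time, that is 1.5 + 0 + 2 = 3.5 h to 1.5 + 0.5 + 2 = 4 h. The remaining 24 − 4 = 20 h to 24 − 3.5 = 20.5 h of the reaction window falls after the infusions end. A reaction in those hours that leads to no further dosing again fits option 1.

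**4. Can one terminated infusion be miscounted as withdrawal?** Protocol 10.7 describes two kinds of path.

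- A Grade 3 or 4 reaction during infusion: the infusion is discontinued and the patient receives no further study drug. The infusion-level and treatment-level meanings agree.
- Other reactions: the infusion is slowed, interrupted, or stopped and restarted. This is option 2.

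What remains is an infusion that is ended, not restarted, and followed by a later dose. The protocol neither describes nor excludes it.

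**5. What else captures the stop?** SAP 8.1 tabulates early termination of study treatment with reasons, by treatment period. Protocol 9.3 records infusion start and stop times and volume. SAP 10.1 summarises cycles received, and SAP 10.2 computes compliance from infused volume. So the fact of stopping, its reason and any partial dose are available. No section states how a disposition reason is tied to a specific AE term, which the SOC and PT table needs.

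**6. Which field feeds the SAP 10.3 table?** The SAP does not say. SAP 6.1 likewise names no source for premature stopping due to an AE.

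**The case against.** The strongest reply is that the label will be understood as intended. Elsewhere the protocol uses withdrawal from study drug to mean that dosing ends for good (7.1.3, 7.4.1.1, 10.7), and 8.3.3.1 asks the investigator to consult before withdrawing drug. An investigator who stops drug on Day 21 for an AE may well choose the option labelled withdrawn, despite the parenthesis. The electronic case report form (eCRF) is not among the documents, and Protocol 17.1.1 says completion instructions will be provided. The form may word the item differently or ask about drug discontinuation separately. This stands as a limit on certainty. It does not remove the mismatch, because the stated definition, if followed, still sends the event to the wrong option.

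A reader might also infer four stronger things that the documents do not support.

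- *That permanent stops between infusions cannot be recorded at all.* Disposition records the stop and its reason. Only a matching AE-level option and a stated link to the AE term are missing.
- *That the withdrawal table will be wrong.* SAP 10.3 does not say it is built from this item, so miscounting is a risk, not a demonstrated result.
- *That terminated infusions would routinely count as withdrawals.* The paths described in Protocol 10.7 leave only the narrow case in step 4, and dosing records would reveal it.
- *That the primary estimand is affected.* SAP 6.1 treats stopping due to an AE as treatment failure but does not refer to the AE action item. The end-of-treatment reason is at least as plausible a source.

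The infusions take about 3.5/672 = 0.52% to 4/672 = 0.60% of a 28-day cycle (672 h). That shows how small a part of the cycle option 3 describes. It does not measure how many events would be misclassified.

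**Conclusion.** The point holds as a mismatch between an infusion-level definition in Protocol 12.2.2.5 and a treatment-level output in SAP 10.3. The likelier error is under-counting of AEs that permanently stop study drug between infusions, with a resulting disagreement between the AE table and the disposition table. Over-counting is confined to an infusion ended and not restarted in a patient who is dosed again.

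The size cannot be estimated from the documents. The conclusion assumes that the protocol definition is carried into the form or its instructions and is followed literally, and that the SAP 10.3 table draws on it. If the table is instead built from the end-of-treatment reason, the count of patients is protected, but the link to the AE term still has to be specified. No effect on the primary analysis is shown.

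**What to change.** - **Protocol 12.2.2.5 and the eCRF completion guideline:** define drug withdrawn as study drug permanently discontinued because of this AE, whenever the AE occurred. Record termination of a single infusion, with later doses given, as a separate option.
- **SAP 10.3:** name the field that identifies treatment-emergent AEs leading to withdrawal of study drug.
- **SAP 6.1:** name the source used to classify premature stopping due to an AE.
- **Before database lock:** reconcile the AE item with the end-of-treatment reason and the dosing records, and query disagreements, including those in records already entered.

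The cost is a completion guideline, one added option and a data-cleaning check. Patient care does not change.

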12.2.2.6 Laboratory and Diagnostic Abnormalities as Adverse Events

Clinically significant abnormal laboratory findings or other abnormal diagnostic assessments (e.g., ECGs, vital signs) that are detected in dosed patients or that significantly worsen relative to baseline in dosed patients will be reported as AEs. Clinical significance is based on the Investigator's judgment but will typically include findings that result in study withdrawal, result in active management of the patient, or are associated with clinical signs and symptoms. Since the study requires patients with elevated or abnormal sUA levels, abnormal sUA levels will typically not be an AE unless judged by the Investigator as being more severe than expected for the patient.

12.2.2.7 **Pregnancy**

While pregnancy itself is not considered to be an AE, any pregnancy complication or elective termination of a pregnancy for medical reasons will be recorded as an AE and followed. The outcome of all pregnancies must be followed up and documented even if the patient is no longer a study patient.

The Investigator, or his/her designee, will collect pregnancy information on every female who becomes pregnant while enrolled in this study and on every female partner of a male patient who becomes pregnant while the male partner is enrolled in this study. The Investigator will report to the Sponsor or Sponsor's designee within 24 hours of learning of a patient's or female partner of a patient's pregnancy. In the case of a female partner of a male participant enrolled in the study becoming pregnant while the male patient is enrolled in this study, a separate pregnancy partner informed consent form will be completed by the patient's partner. The patient or female partner of a patient must also be followed to determine the outcome of the pregnancy. Information on the status of the mother and child will be forwarded to the Sponsor or Sponsor Designee, as appropriate. Follow-up on the child will be to the first well-child visit. Any premature termination of the pregnancy will be reported.

A spontaneous abortion or congenital abnormalities/birth defects will be considered SAEs and will be reported as such. Furthermore, any SAE occurring as a result of a post-study pregnancy and is considered reasonably related to the study drug by the Investigator, will be reported to the Sponsor.

12.2.3 **Reporting Adverse Events**

12.2.3.1 **Adverse Event Reporting Period**

The study period during which AEs must be reported is from the time the patient is dosed until the 30 (\pm 1) days after the last infusion of study drug. During the Screening Phase (from time informed consent is signed up to the time of dosing) any clinically significant changes in the patient's health will be recorded in the patient's medical history and will not be considered as AEs.

Investigators are not obligated to actively seek AEs or SAEs in former study patients. However, if the Investigator learns of any SAE, including a death, at any time after a patient has been discharged from the study, and he/she considers the event reasonably related to the study drug, the Investigator should promptly notify the Sponsor.

12.2.3.2 **SAE Reporting Procedures**

On discovery, all SAEs should be immediately reported (latest within 24 hours of knowledge of the event) to PAREXEL Safety Services by:

Completing the SAE report form and faxing the documents to PAREXEL Safety Services, using the appropriate regional PAREXEL SAE fax numbers below:

NA (Billerica): [contact]

or

Completing the SAE report form and submitting it to PAREXEL Safety Services via email utilizing the address (es) below:

NA: [contact]

In the event that the site is unable to complete the SAE form to report the event within 24 hours of their knowledge of the event, the investigators may report the SAE over the telephone via the SAE answering service, and then provide the completed SAE form via fax or email. If questions arise regarding the reporting procedures or the specifics of the reporting of an event, sites may call utilizing the following numbers:

NA (Billerica): [contact]

The Investigator will complete the SAE form and provide all case information available at the time of the initial report. The investigator must include the following mandatory case information:

1. The patient identification number
2. The event description
3. The seriousness criteria
4. The Investigator's causality assessment

The reporting Investigator must send the written and signed SAE report by facsimile or email, within 24 hours of observing, notification of, or learning of the SAE to PAREXEL Safety Services as described above. Follow-up information regarding an SAE and the supporting data, including laboratory findings and discharge summaries, should be sent by facsimile or email to PAREXEL Safety Services within 24 hours of receipt of the information.

If the Investigator does not have all information regarding an SAE, the Investigator will not wait to receive additional information before completing as much of the form as possible and notifying the safety group. The form will be updated when additional information is received. The Investigator will always provide at minimum: 1) AE term or event name/description, 2) patient identifier, 3) an assessment of causality ([Section 12.2.2.2](#)).

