11.2.2 Gout Flare Assessment

Gout flare will be assessed as part of AE collection with severity determined as described in [Section 12.2.2.3](#). Gout flares will be assessed at each study visit during the Treatment Phase using a validated definition of flares in patients with established gout ([Gaffo 2018](#)). In addition, in an exploratory manner, gout flares will be self-assessed weekly by the patient after randomization and in each Treatment Period using a weekly flare diary ([Poiley 2016](#)).

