12.2.1.1 Adverse Event (AE)

An AE is any untoward medical occurrence associated with the use of a drug (i.e., study drug) in humans, whether or not considered drug related. An AE can therefore be any unfavorable and unintended sign (including an abnormal laboratory finding), symptom, or disease temporally associated with the use of a drug and does not imply any judgment about causality. An AE can arise with use of any drug or medicinal product. A treatment-emergent AE (TEAE) is an AE that starts or worsens at any time after initiation of study drug on Day 0 of Treatment Period 1 until the End of Study Visit (30 days after completion of the last dose of study drug).

Patients will be considered enrolled in the study upon signing the ICF. During the Screening Phase (from time informed consent is signed to immediately before dosing) any clinically significant changes in the patient's health will be recorded in the patient's medical history and will not be considered as AEs. AEs (and thus SAEs) will be collected from the time the patient is dosed (infusion is started) until the end of the End of Study Visit.

12.2.1.2 **Serious Adverse Event (SAE)**

An SAE is any AE that occurs irrespective of study treatment assignment, if it satisfies any of these criteria:

- Results in death;
- Is life-threatening;
- Requires inpatient hospitalization \geq 24 hours or prolongs existing hospitalization;
- Results in persistent or significant disability or incapacity or substantial disruption of the ability to conduct normal life functions;
- Is a congenital anomaly or birth defect;
- Is an important medical event that, based upon appropriate medical judgment, may jeopardize the patient or patient may require medical or surgical intervention to prevent one of the outcomes listed above.

12.2.1.3 **Suspected Adverse Reaction**

A suspected adverse reaction is an AE for which there is a reasonable possibility that the drug caused the AE. For the purposes of IND safety reporting, “reasonable possibility” means there is evidence to suggest a causal relationship between the drug and the AE. Suspected adverse reaction implies a lesser degree of certainty about causality than adverse reaction, which means any AE caused by a drug.

12.2.1.4 **Unexpected Adverse Events and Unexpected Suspected Drug Reaction**

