12.2.4 Follow-up of Adverse Events

The Investigator is required to proactively follow each patient and provide further information regarding AEs and SAEs. All AEs and SAEs will be followed until 30 (+4) days after the last dose of study drug, resolution of the event, until the condition stabilizes, until the event is otherwise explained, or until the patient is lost to follow-up, whichever occurs earlier. Once resolved, the appropriate CRF entries and event reporting forms will be updated, as appropriate.

All AEs and SAEs documented at a previous visit/contact and designated as ongoing will be reviewed at subsequent visits/contacts. The Investigator will ensure that follow-up includes any supplemental investigations as may be indicated to elucidate the nature and/or causality of the AE or SAE. This may include additional laboratory tests or investigations, histopathological examinations, or consultation with other health care professionals.

The Sponsor or the Sponsor's designee may request that the Investigator perform or arrange for the conduct of supplemental measurements and/or evaluations to elucidate as fully as possible the nature and/or causality of the AE or SAE. The Investigator is obligated to assist. If a patient dies during participation in the study or during a recognized follow-up period, the Sponsor will be provided with a copy of any post-mortem findings, including histopathology.

New or updated information will be recorded on the originally completed SAE forms, with all changes signed and dated by the Investigator. This information will also be entered into the CRF.

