Appendix A Schedule of Assessments, continued

Assessment	Scr. - 45 d to D0 (Pre-dose) ³	Treatment Phase														EOS ¹	ET
		TP1 ²		TP2 ²		TP3 ²		TP4 ²		TP5 ²		TP6 ²					
Day	D0	D21	D0 ⁵	D21	D0 ⁵	D21	D0 ⁵	D21	D0 ⁵	D21	D0 ⁵	D7 ⁴	D14 ⁴	D21 ⁴	D28		
Tophus Assessment/Photography	X							X								X	X
Gout Flare Assessment ²²	X	X	X	X	X	X	X	X	X	X	X	X	X	X	X	X	X
Gout Flare Weekly Diary		Continuously on Weekly Basis ²³															X
Joint Assessment (tenderness, swelling)		X						X								X	X
Health Questionnaires ²⁴		X						X								X	X
Collect Sample for sUA	X	Refer to Schedule of Assessments (Appendix B) for sUA Sample Collection during Treatment Phase															X
PD/Uricase Activity Assessment		Refer to Schedule of Assessments (Appendix B) for PD/Uricase Activity Assessments during Treatment Phase															X
Study Drug Administration		Refer to Schedule of Assessments in Appendix B for Study Drug Administration during the Treatment Phase															
Infusion Reaction Follow-up		Refer to Section 12.2.1.5															
Concomitant Medications / Procedures		Continuously														X	X
AE Collection		Continuously														X	X
SAE Collection		Continuously														X	X

1. Phone call at 30 (+4) days after the last study drug infusion for assessment of concomitant medications/procedures, AEs, and SAEs.
2. Visit window at Day 21 of each Treatment Period is +2/-1 days; visit window at Day 7 and Day 14 of Treatment Period 6 is +2/-1 days; visit window at Day 28 of Treatment Period 6 is +3/-4 days.
3. Visit window is -2 days.
4. Assessments at this visit are permitted to be performed remotely (inclusive of collecting applicable lab draws and assessments per protocol visit windows).

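### The documents disagree on when AE reporting ends for patients withdrawn from study drug; read literally, it closes up to 138 days before Day 168, mostly on SEL-212

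*Protocol*

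**What the plan says.** **Text that ties the end to the last infusion**
- Protocol 12.2.3.1 sets the end at 30 (±1) days, counted from the last infusion: "The study period during which AEs must be reported is from the time the patient is dosed until the 30".
- Protocol 12.2.1.1, repeated in SAP 10.3: a TEAE starts or worsens after first dosing, "until the End of Study Visit (30 days after completion of the last dose of study drug"; no tolerance is given.
- Protocol Appendix A, footnote 1 (the EOS contact): "Phone call at 30 (+4) days after the last study drug infusion for assessment of concomitant medications/procedures, AEs, and SAEs".
- Protocol 12.2.4, on following up events already recorded: "All AEs and SAEs will be followed until 30 (+4) days after the last dose of study drug", or an earlier resolution or stabilisation.

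**Text that points to a later end**
- Protocol 7.1.3: "If withdrawn from study drug, regardless of reason, the patient will continue study visits to the end of Treatment Period 6". The same section places the EOS telephone visit at completion of the 6-month Treatment Phase, or at early termination if consent is withdrawn.
- Protocol 8.3.2 anchors study completion at 30 (+4) days after the TP6 Day 0 visit.
- Protocol 12.2.1.1 also says that AEs and SAEs "will be collected from the time the patient is dosed (infusion is started) until the end of the End of Study Visit".
- Protocol 7.1.2 has AEs monitored continuously during the study, and the Appendix A grid shows AE and SAE collection as continuous.

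**Gout flares**
- Protocol 11.2.2: "Gout flare will be assessed as part of AE collection", with AE severity grading. Section 10.6.1 has flares recorded as AEs.
- Section 11.2.2 and Appendix A also require a flare assessment with a validated definition at each visit, through TP6 Day 28. A weekly diary is exploratory.
- Flare incidence over TP1-6 and over TP1-3 are key secondary endpoints. Both use treatment policy except for death, and both divide the flare count by length of observation (Protocol 13.4.2; SAP 6.2.8 and 6.2.9). SAP 9.3.2.8 and 9.3.2.9 do not name the data source.

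**The concern.** For a patient who takes all six doses, 30 days after the last infusion and the end of TP6 nearly coincide, so the choice of anchor does not matter. For a patient taken off drug early they can be months apart, and the documents do not say which one governs.

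The sUA stopping rule in Protocol 7.4.1.1 requires a value below 2.0 mg/dL one hour after the first dose. Patients enter with a Screening sUA of at least 7 mg/dL, so someone on saline should almost never meet that condition. Early stops, and therefore short AE windows, should be concentrated in the SEL-212 arms.

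TEAE tables report crude numbers and percentages of patients (Protocol 13.5.2; SAP 10.3), and Protocol 13.5.2 adds relative risks against placebo. If one side of that comparison is ascertained for a shorter time, it looks safer than it is. For example, the post-baseline chest X-ray for interstitial lung disease, which is an AE of special interest, is taken at six months or early termination. A finding at Day 168 in a patient whose only dose was in TP1 lies well outside the TEAE window.

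**Working it through.** **Reproducing the plan's own durations.** The Treatment Phase is 6 × 28 = 168 days, as stated. The longest participation is 45 days of screening + 5 × 28 = 140 days to the last infusion + 30 = 215 days, matching the protocol's upper figure. Counting the 30 days from the end of the Treatment Phase would give 45 + 168 + 30 = 243, which does not match. So for a patient with all six doses, EOS falls at Day 140 + 30 = 170, just after Day 168, and both anchors agree.

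**Gap for early stops.** For a last infusion in TPk on the nominal 28-day schedule:
- last infusion day = 28 × (k − 1)
- window end = last infusion day + 30
- gap = 168 − window end

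The range column uses 34 days (the +4 tolerance) and 29 days (the −1 tolerance) in place of 30.

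| Last dose in | Last infusion day | Window end (day) | Gap to Day 168 (days) | Range over tolerances | Gap as share of 168 days |
|---|---|---|---|---|---|
| TP1 | 0 | 30 | 138 | 134-139 | 82% |
| TP2 | 28 | 58 | 110 | 106-111 | 65% |
| TP3 | 56 | 86 | 82 | 78-83 | 49% |
| TP4 | 84 | 114 | 54 | 50-55 | 32% |
| TP5 | 112 | 142 | 26 | 22-27 | 15% |
| TP6 | 140 | 170 | none | none | 0% |

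The different tolerances move the window end by at most 34 − 29 = 5 days. They are untidy, but they do not create the gap; the anchor does.

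**Flare endpoints.** If flares were taken only from AE records kept within the literal window, the TP1-6 endpoint would have the gaps above. The TP1-3 endpoint ends at 3 × 28 = Day 84, so its gaps would be 84 − 30 = 54 days (last dose TP1), 84 − 58 = 26 days (TP2) and none from TP3 onward. The denominator would keep running if length of observation counted the off-drug visits. This calculation depends on the data source, which the SAP leaves open.

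**Exposure-adjusted rates.** SAP 10.3 divides by treatment exposure time. If event collection is extended to the end of TP6 while that denominator stays as it is, events arising off drug are divided by time on treatment only, and rates in the arms with more early stops are inflated. Numerator and denominator have to be changed together.

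**The case against.** The strongest reply is that the longer reading is already in the protocol. AE collection runs to the end of the EOS visit, Section 7.1.3 puts that visit at completion of the 6-month phase, AEs are monitored continuously, and off-drug patients keep attending visits. SAP 10.3 also summarises all AEs as well as TEAEs and lists non-TEAEs, so events after the TEAE window have a place to go. That is a fair reading, and it is why this is a contradiction and not a defined cut-off. It does not settle the matter. The section that tells sites what must be reported uses the last infusion, the SAP can tabulate only what sites record, and the TEAE definition excludes late events whichever reading sites follow.

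Four stronger readings are tempting and are not supported:
- **That flares cease to be captured about 30 days after the last dose.** Visit-based assessment runs to TP6 Day 28 for all patients, and Section 10.6.1 sets no time limit on recording flares as AEs. What remains is a risk, because flares are also AE records, severity is graded through the AE system, and the SAP names no source.
- **That only SEL-212 patients are affected.** Placebo patients can also come off drug: for a missing Day 21 sUA (7.4.1.1), for severe or critical COVID-19 or certain COVID-19 treatments (12.1.8.7), or after a Grade 3 or 4 infusion reaction (10.7). Predominantly SEL-212 is defensible; exclusively is not.
- **That flare incidence is understated by a calculable percentage.** This needs the share of each arm stopped, the timing of the stops and the absence of any other flare capture. The documents give neither of the first two for this trial and contradict the third.
- **That the conflicting tolerances are the main problem.** They account for at most 5 days, and Section 12.2.4 governs follow-up of known events, so it is not a like-for-like conflict with 12.2.3.1.

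**Conclusion.** The documents contradict each other on when AE reporting ends for patients withdrawn from study drug. On the literal wording of Section 12.2.3.1, mandatory reporting and TEAE status end 138, 110, 82, 54 or 26 days before Day 168 for a last dose in TP1 to TP5, with no gap for TP6. These figures assume nominal 28-day dosing and a 30-day window; dosing windows and extended periods would shift them.

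Because early stops should fall mainly on SEL-212, crude TEAE counts and relative risks against placebo could be biased in its favour. The direction follows from the stopping rule. The size at arm level cannot be stated from the documents. The safety consequence is the firmer one; the flare consequence depends on which records the flare endpoints use.

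**What to change.** - **One end date.** Reconcile Protocol 7.1.3, 8.3.2, 12.2.1.1, 12.2.3.1, 12.2.4 and Appendix A, and SAP 10.3, so that AEs are collected to the later of the end-of-TP6/EOS contact and 30 (+4) days after the last infusion.
- **Two sets of AE tables.** Tabulate on-treatment AEs (to 30 days after the last dose) separately from all AEs to the end of study.
- **Matching denominators.** In SAP 10.3, pair rates based on treatment exposure time with on-treatment events only, and use observation time for the whole-study rates.
- **Named flare source.** In SAP 9.3.2.8 and 9.3.2.9, state that flares come from the visit flare assessments through the end of the endpoint period, whatever their TEAE status, with an observation-time denominator covering the same span.

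The cost is protocol and SAP wording plus a small amount of extra tabulation. The visits that would supply the data are already scheduled.
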